9.1 SOP Recruitment of participants for clinical trials

Standard Operating Procedure (SOP) Recruitment of participants for clinical trials

Purpose and scope

This SOP describes the procedures that all study personnel will use in recruiting participants while fulfilling ethical responsibilities for protecting the rights and welfare of participants as part of PATHWAY-27 WP5.

Responsible persons

Principal Investigator

In each investigating centre, the Principal Investigator will be responsible and accountable for:

1. Getting approval from the PATHWAY-27 and relevant ethics committees of the methods to be used to recruit participants, including review and approval of recruiting materials.
2. Assuring that all participants understand the purpose of the study, its risks and benefits.
3. Assuring that all participants understand what is expected of them (number of visits, types of examinations, dietary and lifestyle restrictions, intervention).
4. Assuring that the participants understand that they may withdraw from the study at any point, but need to inform the research team.
5. Assuring that all participants meet eligibility criteria as specified in the study protocol.
6. Assuring that all participants have given informed consent prior to study procedures being performed.
7. Maintaining accurate and complete records of potential and enrolled study participants.
8. Informing participants of the termination or cancellation of the research trial.
9. Informing participants of any approved deviation from the protocol.
10. Informing participants of any remuneration to recompense their participation, or reimbursement of expenses, when applicable.
11. Reporting accurately to the work package leader for continuing review.

The principal investigator may delegate responsibility for recruiting and enrolling participants to other qualified researchers involved in the study, but may not delegate accountability.

Clinical Researcher

The clinical researcher may be given the responsibility for:

1. Monitoring the progress in recruiting patients.
2. Keeping records of subject recruitment.
3. Informing the principal investigator about progress toward recruitment goals.
4. Verifying and reviewing each participant's information/history for eligibility criteria, and informing the principal investigator if the participant's information changes during the trial.

Procedures

Recruitment strategies

1. Participants can be recruited from a variety of sources including internet and paper postings, written media advertisements, television/radio advertisements, from support groups, health fairs, or from local hospitals and clinics via clinician deferral.
2. The principal investigator or the clinical researcher will enter in the EDC system subjects satisfying to entry criteria.

3. When applicable, researchers who get referrals from clinician colleagues may not contact these referrals directly. The clinicians may inform their patients of the research and advise their patients to contact the researcher.
4. Financial or other incentives provided to research staff or physicians by sponsors based on numbers of participants recruiting or enrolled are strictly prohibited.
5. Recruitment Materials
6. Any materials directed to participants or the general public with the intent of recruiting them to participate in clinical research must be approved by the PATHWAY-27 ethics committee and submitted to the relevant ethics committee for review and approval. Similarly these materials will have to be approved by the local ethics authorities. These include announcements, advertisements, flyers/posters, phone scripts for screening, radio and television announcements, notice board tear-offs, Internet postings.
7. Copies of approval from the REC (Research Ethics Committee) will be provided to the European Commission prior to commencing the research.
8. Advertisements may include:
 - a. A statement that the study involves research
 - b. A brief description of the purpose of the study, including details of the clinical disorder that the study is investigating
 - c. Eligibility criteria (in summary form)
 - d. A truthful description of potential benefits, if any, to the subject from study participation
 - e. The name of the institution conducting the study
 - f. The name of the sponsor providing finance for the study
 - g. The name and phone number of person to be contacted for further information
9. Advertisements may not include:
 - a. Any expressed or implied claim that the research will improve the subject's medical condition
 - b. Expressed or implied statement that the research is endorsed by the medical profession or any medical or government or professional bodies
10. Any questions about criteria should be referred to the principal investigator. All such contacts/discussions must be recorded.

Enrolment Procedures

1. Before enrolment, the Clinical Researcher must ensure that the subjects meet the eligibility criteria (inclusion and exclusion criteria).
2. The Clinical Researcher will keep records of recruitment and monitor and will inform the principal investigator of progress in recruiting participants. Every person who is considered a potential candidate for the study should be entered in the Screening and Enrolment Log (based on study inclusion and exclusion criteria). It should be noted whether individuals have enrolled in the study and, if not, the reason should be documented.
3. At the screening visit, the potential participant must give informed written consent prior to any screening procedures. Signed informed consent forms from all subjects who entered the screening process should be retained for the duration of the study including the ones who terminated their participation in the study during the screening process.
4. After screening and randomization, the participant's code/ID number should be entered in the Screening and Enrolment Log. The Enrolment Log can serve as the coded subject list, which must be archived at the end of the study. The Screening and Enrolment Log must include details of all subjects randomized in the trial, with subject name, address, and year of birth, code.
5. Recruitment rates should be regularly evaluated during the recruitment period, with reassessment of the strategy when recruitment targets are not being met.

9.2 Information for participants

9.4 SOP Collection of blood by venepuncture from fasted subjects and preparation of serum

Standard Operating Procedure (SOP) Collection of blood by venepuncture from fasted subjects AND preparation of serum

Purpose and scope

This SOP describes the procedures that all study personnel will use for collecting peripheral blood samples by venipuncture from fasted study subjects, and preparation of serum needed for laboratory testing, as specified in the PATHWAY-27 WP5 human study protocol, with proper specimen identification and handling, while ensuring the safety of subjects and staff.

Responsible persons

Principal Investigator

The Principal Investigator is responsible and accountable for:

1. Checking that the phlebotomist has the necessary and up-to-date training required by the local authorities for blood collection procedures.
2. Ensuring that all materials and equipment required for the procedure are available and in good working order for use by the phlebotomist.
3. Ensuring that a suitable dedicated area is available for blood collection.

Clinical Researcher

The clinical researcher may be given the responsibility for:

1. Ensuring that subjects are aware of the prerequisite conditions.
2. Ensuring that all samples are correctly labelled.
3. Keeping records of samples collected including subject's code, date, storage and analysis information.
4. Informing the principal investigator about any issues that may arise during the collection of blood samples.

Phlebotomist

The phlebotomist will be responsible for:

1. Ensuring that all blood collections are done in a manner that maximizes the safety of the subject, himself and any other staff or person present during blood collection.
2. Reporting any accidents or incidents that may occur during blood collection.

Materials and equipment

Disposable gloves

Disinfecting spray (isopropyl alcohol) for disinfecting surfaces

Disinfecting swabs (chlorhexidine gluconate, isopropyl alcohol, isopropyl alcohol)

Tourniquet

Vacutainer/Sarstedt specimen tubes

Vacutainer/Sarstedt holders

Appropriate size sterile disposable needles

Cotton balls/swabs

Sharps disposal container for clinical waste and clinical waste bags

Markers

Refrigerator
Refrigerated centrifuge

Procedures

Subject prerequisites

The clinical researcher must ensure that subjects are aware of the pre-requisite conditions for blood collection, and should check with the subject that these were complied with using a checklist. Conditions include:

1. The subject should be fasted for at least 10 hours, and not more than 14 hours, prior to blood collection.
2. The subject should refrain from consuming alcohol during the evening before blood collection.
3. The subject should refrain from partaking in strenuous exercise the evening before and in the morning before blood collection.

Before blood collection

- Ensure the area designated for blood collection is clean. Disinfect tables and trays as defined by local hygiene plan before each blood draw.
- Ensure that all materials and equipment is available, assembled and in good working order.
- Ensure that only new sterile, single use needles and tubes are used for each blood draw, ensure that the packaging has not been opened or tampered with. They are never to be cleaned and reused for any purpose.
- Check what the blood is to be used for to confirm the quantity of blood to be drawn and which kind of tubes to use.
- Verify the identity of the subject before any procedure commences.
- Install the subject in a comfortable chair or on a medical bed with the extremity from which blood will be drawn supported on a sturdy table or other support. The preferred sites for phlebotomy are the median antecubital veins of the upper extremity. Veins on the dorsum of the hand and other forearm veins are possible alternative sites.
- Explain the blood drawing procedure to the subject and reassure him/her for safety.
- Tubes or other specimen containers should be labelled immediately before sample collection. Do not prepare tubes for more than one subject at a time.
- Blood collection:
 - The phlebotomist should wear disposable gloves and use an aseptic technique during phlebotomy. Gloves should always be worn when handling or transporting specimens if there is any possibility of direct contact with blood or other body secretion.
 - A tourniquet may be used to transiently distend veins prior to drawing blood. Do not leave the tourniquet longer than it is necessary.
 - Using the tip of the index finger, examine the phlebotomy site, feel the vein, and decide exactly where to place the puncture.
 - Disinfect the phlebotomy site by swabbing the skin in small outward circles with an alcohol swab. Do not touch the prepared puncture site with your fingers after disinfecting the skin.
 - Using aseptic technique, insert the needle of the vacutainer/sarstedt device into the vein. If possible, always allow the full amount of blood to be drawn by each evacuated tube when using the vacutainer/sarstedt system tubes.
 - After drawing, carefully mix the blood in tubes containing additives by inverting the tubes several times. After serum preparation, place the tubes in suitable bags, and if possible store at 2-8 °C until further use.
 - After drawing the required blood samples, release the tourniquet. Remove the needle from the vein, cover the puncture site with a cotton swab, and hold until adequate haemostasis is visible.

- After completion, needles must be properly disposed of in a puncture resistant container to be destroyed by incineration. Any other non-sharp material that has been in contact with blood fluids must be disposed by incineration in a suitable holding bag.

Discontinuation of the procedure during blood collection

- The procedure may be stopped if:
- The subject becomes distressed. In which case remove the needle only when it is safe to do so.
- There is any breach of protocol or event that compromises the safety of the subject or the phlebotomist. Inform the clinical researcher immediately.

Labelling

Appropriate labelling of the tubes is essential for appropriate handling and analysis of the samples, ensuring that samples are not wasted unnecessarily.

Each tube must be clearly labelled with:

- Date of collection
- Time of collection
- Subject's code
- Type of analyses to be performed or barcode that includes these informations according to operating lab.

In LIGHT, tubes must be placed inside polyethylene bags, sealed and labelled.

Preparation of serum

Some analyses require the use of serum. Serum will be prepared according to the following procedure:

1. Blood samples will be allowed to clot for 30 minutes at room temperature in the collection tubes (no heparin).
2. Centrifuge the tubes for 10 min at 820 RCF at 4°C.
3. Collect the supernatants in suitable new, sterile and tubes labelled as described above.
4. Store at -80°C if storage is required.
5. Discard old tubes with blood cells and remnants in a clinical waste bag and destroy by incineration.

Reporting

Any accident or mishap will be reported to the principal investigator.

9.5 SOP Quantification of HDL-cholesterol in serum samples

Standard Operating Procedure (SOP) Quantification of HDL-cholesterol in serum samples

Purpose and scope

This SOP describes the procedures that all study personnel will use when analyzing serum samples for the quantitative determination of serum HDL-cholesterol as part of PATHWAY-27 WP5, while ensuring the safety and welfare of subjects and staff involved in the study.

Responsible persons

Principal investigator

The principal investigator is responsible and accountable for:

1. Ensuring that the equipment is fit for purpose
2. Ensuring that all staff is suitably trained in all aspects of the procedure, including the safe handling of blood-derived samples and chemicals.
3. Notifying the WP leader of any deviations, safety breaches or abnormal results.
4. Keeping record of the code of all subjects entering the study, guaranteeing their data will be anonymous

Clinical researcher or manager

The clinical researcher or manager is responsible for Reporting to the principal investigator the results of analysis and logs of all procedures undertaken, highlighting any deviations, safety breaches or abnormal results

Operator

The operator is responsible for:

1. Following all procedures according to the SOP and instructions provided, including the keeping of logs of calibration and control procedures.
2. Notifying the clinical researcher/manager or principal investigator of any deviations or abnormal results.

Procedures

Name of the method

Automated enzymatic colorimetric method for determination of HDLcholesterol.

Purpose

For the in vitro diagnostic use in the quantitative determination of HDL-cholesterol from serum using an automated blood analyser.

Principle

The method is a two-stage reaction. In the first step, non-HDL cholesterol is enzymatically released and eliminated. In the second step, HDL-cholesterol is specifically released using a surfactant. Cholesterol is de-esterified using cholesterol esterase to form free cholesterol and fatty acids. Cholesterol is then enzymatically oxidised to cholesten-3-on and hydrogen peroxide (catalysed by cholesterol oxidase). Hydrogen peroxide can be measured following a Trinder

endpoint reaction (catalysed by catalase), the products of which can be detected by colorimetry at wavelengths >505 nm.

Equipment

Automated blood analyser. Manufacturer varies between countries therefore cannot be harmonized. However, the analyses will focus on variations of this parameter from d0 to d28 that would not be affected by the lack of analyser harmonisation.

Reagents

Reagents will be purchased, prepared and stored according to the equipment manufacturer's instructions.

Calibration of the equipment

The equipment should be calibrated according to manufacturer's instructions. Calibrations will be performed:

- Every time that the equipment is switched off
- Every time that the equipment is cleaned or maintained
- Every time that any trouble shooting procedures have been undertaken
- Every time that any of the reagents or optical components are changed
- Each instrument brand/model will have a maximum calibration stability that should be complied to. Calibration standards will be applied according to manufacturer Instructions. A log of calibrations will be kept including the date, the lot number of the reagents used, the date the reagents were first opened and their expiry date.

Quality control

Appropriate control tests will be routinely performed using control samples (upper and lower limit controls). Each laboratory may have its own quality control procedures, but as a minimum, these control tests will be performed:

- Twice daily
- After each calibration
- If there are any issues with analyses that suspect deviations from the normal range of analysis
- Quality control standards will be purchased and used according to the manufacturer's instructions. A log of quality control tests will be kept including the date, the lot number of reagents used, the date the reagents were first opened, and their expiry date.

Samples

Serum will be used for analysis.

- Sera will be collected, prepared and stored according to SOP.
- Before analysis, the operator will check that check the tubes for signs of leakage or contamination, and that the labelling is correct for the type of test requested. The operator shall keep a record of the samples analysed by subject's code.
- Minimum volumes drawn will be in accordance with manufacturer instructions.
- There are no significant interfering molecules within serum, but some chemical substances may interfere with catalase activity (e.g. sodium azide), therefore unprocessed/unadulterated serum will be used.
- For details of how the serum should be handled and loaded onto the machine, please adhere to manufacturer's instructions.

Range of analysis:

For serum samples, the method is linear for the following range:

5–115 mg/dL or 0.1–3.0 mmol/L

Conversion factor: mg/dL x 0.0259 = mmol/L

Precision

Each instrument will have specific performance ranges, but generally the percentage coefficient of variation (%CV) should be below 3%. Replicate analyses will be performed for each sample.

Expected values

Low (undesirable, high risk): < 40 mg/dL (< 1.0 mmol/L) for men < 50 mg/dL (< 1.0 mmol/L) for women

There is no clinical significant value at which medical team should be contacted.

HDL-cholesterol values are not affected by fasting.

Recording of results

Results will be collected by the clinical researcher and entered into the database for statistical analyses. Any abnormal results will be reported to the principal investigator.

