Blood will be sampled after an overnight fast (10 to 14 hours). Serum will be obtained by centrifugation at 4°C 20 min 1800g, immediately shipped to the accredited analysing lab or aliquoted and stored at -80°C until further analysis. Cellular fractions will be discarded and destroyed by incineration. Triglycerides, HDL-cholesterol and glucose will be measured by internationally validated standard enzymatic assays. The analysing lab is responsible for proper disposal of the biological material according to local rules. Biological materials will be kept until the publication of the study in order to be able to perform eventual control measurements. Thereafter, the analysing lab is responsible for proper disposal of the biological material according to local rules.

5.8 *Compliance assessment*

Compliance will be assessed after collection of all food packages on day 28 and using a record that participants are asked to complete during the trial.

6. Statistical considerations

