Each instrument will have specific performance ranges, but generally the percentage coefficient of variation (%CV) should be below 4%. Replicate analyses will be performed for each sample.

Expected values

Normal fasting < 150 mg/dL (<1.70 mmol/L)

Normal non-fasting: < 250 mg/dL (< 2.83 mmol/L)

Borderline high: 250–500 mg/dL (2.83–5.65 mmol/L)

Hypertriglyceridemia: > 500 mg/dL (> 5.65 mmol/L)

High risk for pancreatitis: > 1000 mg/dL (> 11.30 mmol/L)

Triglyceride levels > 1000 mg/dL will be notified to the participant medical doctor.

Recording of results

Results will be collected by the clinical researcher and entered into the database for statistical analyses. Any abnormal results should be reported to the principal investigator.

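### The lipid SOPs treat the day 1 to day 28 change as immune to analyser differences, which holds only for a constant offset; a between-visit assay shift can bias within-arm changes and the matrix effect, but not the choice of BEF within a matrix

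*Protocol*

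**What the plan says.** Sections 9.5 (HDL-C) and 9.6 (TG), under Equipment, explain why the centres use different analysers: "Manufacturer varies between countries therefore cannot be harmonized". Both go on to say that "the analyses will focus on variations of this parameter from d0 to d28 that would not be affected by the lack of analyser harmonisation".

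On sample handling, section 5.7 allows two routes: serum is "immediately shipped to the accredited analysing lab or aliquoted and stored at -80°C until further analysis". Neither 5.7 nor the SOPs say whether a participant's two samples must share a route, run, calibration or reagent lot.

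The SOPs do contain laboratory controls:
- Recalibration after switch-off, cleaning or troubleshooting, and also "Every time that any of the reagents or optical components are changed". Reagent lots are logged.
- Control samples at least twice daily and after each calibration, with local freedom above that floor: "Each laboratory may have its own quality control procedures, but as a minimum, these control tests will be performed".
- Precision for HDL-C: "generally the percentage coefficient of variation (%CV) should be below 3%. Replicate analyses will be performed for each sample". For TG: "generally the percentage coefficient of variation (%CV) should be below 4%. Replicate analyses will be performed for each sample".

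The primary endpoints in section 6.4 are the mean changes in TG and HDL-C, modelled with food matrix and type of enrichment as fixed effects. Mean changes from baseline are also presented with 95% CIs. Each matrix is studied in one centre (sections 1 and 4). Each centre randomises five arms in blocks of five (6.1), and there is no placebo or control product (5.1).

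**The concern.** The SOP sentence is the protocol's stated reason for not needing harmonised analysers in a three-centre study whose primary endpoints are change scores. The algebra supports it only in one case, a fixed additive offset. Two other kinds of analytic error survive subtraction: a proportional difference in calibration, and a shift in one laboratory between a participant's first and last visit. The sentence is about the first situation (different analysers in different countries). The second is a neighbouring gap that the SOPs leave open, because nothing puts both sera on one calibration and lot.

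What is at stake differs by output. The within-arm mean change has no placebo change to subtract, so a laboratory shift goes into it in full. The matrix effect compares laboratories, so it absorbs any difference in shift between them. The comparison among the five enrichments within a matrix is made inside one laboratory.

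**Working it through.** The protocol gives no power, effect size, SD of change or drift figure (section 3.2 states only 20 per arm), so there is no planned figure to reproduce. Below, the CV limits and metabolic-syndrome cut-offs come from the protocol. The shift sizes and SDs of change are assumptions.

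**1. What subtraction removes.** Write the reading at visit v as a + b_v × true value.
- If b is 1 at both visits, a cancels and the SOP sentence is exact.
- If b differs from 1 but is equal at both visits, the change is multiplied by b. With b = 0.95 or 1.05, a TG change of -15 mg/dL reads as -14.25 or -15.75.
- If b moves by a fraction s between visits, the change gains about s × level.

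**2. Size of a shared shift in a mean change (s × level).**
- HDL-C at 40 mg/dL: 1% gives 0.4 and 3% gives 0.03 × 40 = 1.2 mg/dL.
- TG at 150 mg/dL: 1% gives 1.5 and 4% gives 0.04 × 150 = 6.0 mg/dL.

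**3. Effect on a within-arm 95% CI, n = 20.** Coverage is taken from the noncentral t distribution with 19 df and noncentrality shift/(SD/√20).
- HDL-C shift 1.2 mg/dL: coverage about 75%, 86% or 90% for an assumed SD of change of 4, 6 or 8 mg/dL.
- HDL-C shift 0.6 mg/dL: 90-94% over the same SDs.
- TG shift 6 mg/dL: 86-93% for an assumed SD of 30-60 mg/dL.

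**4. Noise in the comparison of two arms.** Take the extreme case: single determinations, analytic error at the CV limit, all of it between runs. The analytic SD of a change is √2 × CV × level.
- HDL-C: √2 × 0.03 × 40 = 1.70 mg/dL. TG: √2 × 0.04 × 150 = 8.49 mg/dL.

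Detectable difference (80% power, two-sided 5%, 20 per arm) = (1.960 + 0.842) × √(2/20) × SD = 0.886 × SD.

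| Endpoint | SD without analytic error (assumed) | SD with it | Detectable difference, with | without |
|---|---|---|---|---|
| HDL-C | 4 | 4.35 | 3.8 | 3.5 |
| HDL-C | 6 | 6.24 | 5.5 | 5.3 |
| HDL-C | 8 | 8.18 | 7.2 | 7.1 |
| TG | 30 | 31.2 | 27.6 | 26.6 |
| TG | 45 | 45.8 | 40.6 | 39.9 |
| TG | 60 | 60.6 | 53.7 | 53.2 |

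The gain is a ceiling, because within-run error would remain after pairing.

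**5. Bias by type of comparison (simulation, 4,000 trials).** HDL-C mean 42 mg/dL (SD 6), SD of change 5, no true effect, 100 participants per centre in blocks of five. Arms were compared by a five-arm F test in one centre. The matrix contrast was a two-sample t test between two centres, standing in for the matrix term of the planned model.

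| Scenario | Bias, within-arm change | Bias, arm difference | F test rejects | Matrix test rejects |
|---|---|---|---|---|
| No shift | 0.01 | 0.00 | 5.0% | 4.5% |
| 3% day-28 shift, one centre | +1.28 | 0.00 | 5.2% | 42.9% |
| Random run shifts, SD 3%, shared by 10 consecutive participants | -0.02 | 0.00 | 3.4% | 16.1% |

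The +1.28 agrees with 0.03 × 42 = 1.26. A shift shared by all arms of a centre cancels between arms and stays in everything else.

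**The case against.** Four points can fairly be made against this.

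First, the SOP sentence concerns analysers in different countries, not drift in one laboratory, and drift is not ignored: control samples follow every calibration, lots are logged, CVs are capped and samples are replicated. This stands. What is missing is narrower, namely any rule or limit that ties a participant's two readings together.

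Second, a reader might infer that the two visits are necessarily read under different calibrations, or that a centre may ship one sample fresh and freeze the other. The documents do not support this. They are silent on pairing, and the frozen route would equally allow both sera to be run together. Separate runs are permitted, not prescribed.

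Third, a reader might infer that drift distorts the selection of the best BEF, or that pairing would buy a large gain in precision. Neither follows. The selection is made within one centre among blocked arms, where a shared shift cancels if assay timing is unrelated to arm. The gain in detectable difference is a few tenths of a mg/dL for HDL-C at most and about 1 mg/dL for TG.

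Fourth, the simulated bias in the within-arm change assumes that every day-28 sample in a centre is shifted. With staggered entry, a single calibration step touches only participants whose two visits straddle it, so the bias would be smaller. In an exploratory study without placebo, the within-arm change is also largely descriptive, and matrix is confounded with centre whatever the laboratory does. These points lower the stakes but do not make the SOP sentence correct, and the within-arm CIs are still to be reported.

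**Conclusion.** The SOP statement is too strong. It holds for a constant additive offset and fails for a proportional analyser difference or a between-visit shift. The protocol leaves room for such a shift by permitting separate runs and setting no between-visit limit.

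The consequence is confined to two outputs. Within-arm mean changes and their 95% CIs can be biased by up to about 1.2 mg/dL for HDL-C at 40 mg/dL or 6 mg/dL for TG at 150 mg/dL if the assumed shift reaches the SOP precision limit and affects all day-28 samples. Smaller or partial shifts do proportionately less. The matrix effect can be biased by the same mechanism, on top of its existing confounding with centre and laboratory.

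The within-matrix choice of BEF is not biased, on the condition that assay timing is unrelated to arm, and loses little precision: at mid-range assumed SDs of 6 and 45 mg/dL, the detectable difference would improve at most from 5.5 to 5.3 mg/dL (HDL-C) and from 40.6 to 39.9 mg/dL (TG). The documents give no drift size and no SD of change, so all these magnitudes are conditional. It is a cheap improvement worth making, not a threat to the pilot's main decision.

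**What to change.** In section 5.7 and SOPs 9.5 and 9.6:
- Require that each participant's day-1 and day-28 sera follow the same handling route, are stored at -80°C, and are assayed for TG and HDL-C in the same run, with one calibration and one reagent lot, blind to arm.
- Reword the sentence under Equipment so that it claims only that a constant offset, equal at both visits, cancels in the change.

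In section 6.4, state that differences between matrices cannot be separated from differences between centres and analysers. Paired runs do not cure that, nor do they remove a proportional difference between analysers.

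The cost is small. Storage at -80°C is already foreseen in 5.7, and lipids are already measured at the Visit 1 screening, so eligibility need not wait for the paired assay. The real downsides are that endpoint lipids arrive later, and that any prompt assay kept for the existing notification and abnormal-result reporting means some samples are assayed twice.
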